1.3 Secondary Study Endpoints

The secondary objective of this pilot study is to evaluate the safety of daily administration of liraglutide in humans seeking treatment for an OUD.

1) Cardiorespiratory Function

- a. *Blood Pressure*. Change in blood pressure from baseline (Day 1) to: i) the beginning of each study drug dose (Days 2, 8, 14, 20, 26); ii) end of the target drug dose (Day 19 [Day 31 for 5-dose intervention]); and iii) rebound follow-up (Day 21 [Day 33 for 5-dose intervention]).
- b. Heart Rate. Change in heart rate from baseline (Day 1) to: i) the beginning of each study drug dose (Days 2, 8, 14, 20, 26); ii) end of the target drug dose (Day 19, [Day 31 for 5-dose intervention]); and iii) rebound follow-up (Day 21 [Day 33 for 5-dose intervention]).
- c. *Respiration*. Change in respiratory from baseline (Day 1) to: i) the beginning of each study drug dose (Days 2, 8, 14, 20, 26); ii) end of the target drug dose (Day 19 [Day 31 for 5-dose intervention]); and iii) rebound follow-up (Day 21 [Day 33 for 5-dose intervention]).

- 2) **Body Weight** (*kg*). Absolute and percent change in body weight from baseline through the end of rebound follow-up (Daily, from Days 1 to 21 [Days 1-33 for 5-dose intervention]).
- 3) **Glycemic Control.** Glycemic control will be monitored by fasting blood samples for fructosamine and A1c. Fasting blood sample measurements change slowly overtime (i.e., across weeks and months) and therefore will be evaluated only on Days 2 and 19 [and additionally Day 31 for 5-dose intervention] via venipuncture.
- 4) Adverse Events. Frequency of adverse events (AE) and serious adverse events (SAE) deemed related to treatment throughout the study period (Days 1-21 [1-33 for 5-dose intervention]), and at 30 days post-intervention (Day 49 [Day 61 for 5-dose intervention]).

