1.4 Exploratory Endpoints

- 1) **Prefrontal Cortical Response to Drug Cues.** Change in blood oxygenation level response to visual opioid drug cues in prefrontal cortex from baseline (Day 1) to end of the target drug dose (Day 19 [additionally Day 31 for 5-dose intervention]) using Functional Near Infrared Spectroscopy (fNIRs).
- 2) **Rebound Ambient Drug Craving.** Change in ambient drug craving as measured by 0-100 VAS delivered via smartphone using the EMA on test days and on the first two days and last 2 days of each treatment dose from end of rebound follow up (Day 21 [Day 33 for 5-dose intervention]) to baseline (Day 1) and to end of the target drug dose (Day 19 [Day 31 for 5-dose intervention]).
- 3) **Rebound Blood Pressure.** Change in blood pressure from end of the target drug dose (Day 19 [Day 31 for 5-dose intervention]) to rebound follow up (Day 21 [Day 33 for 5-dose intervention]).
- 4) **Rebound Heart Rate.** Change in heart rate from end of the target drug dose (Day 19 [Day 31 for 5-dose intervention]) to rebound follow up (Day 21 [Day 33 for 5-dose intervention]).
- 5) **Rebound Respiration.** Change in respiratory from end of the target drug dose (Day 19 [Day 31 for 5-dose intervention]) to rebound follow up (Day 21 [Day 33 for 5-dose intervention]).
- 6) **Long-term Glycemic Control.** Change in HbA1c and fructosamine levels from Day 2 to end of the target drug dose (Day 19 [Day 31 for 5-dose intervention]).

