Data reduction including derivation of summary features for continuously collected data (e.g., sleep data, physiological data) will be performed before formal statistical analysis. Descriptive analysis will be performed to explore distributions of data and identify potential outliers. Assumptions and goodness of fit of statistical models will be assessed. Missing data, including mobile and ambulatory attrition and drop-out will be examined to ensure the validity of statistical models used. Because ambulatory and mobile monitoring will continue during laboratory assessment days, correlation analyses will be used to confirm the agreement between corresponding measures from the two approaches; this will both speed harmonization for follow-up analyses, and provide additional validation of the measures used in the both cases.

The primary endpoints of the EMA assessment will be the rate of reduction of craving across the approximately 21 day study period in the treatment condition compared to the control condition while controlling for the traditional craving triggers of sleep, stress, hunger, affect, and pain and discomfort. Sleep and activity will be measured using a multimodal approach with self-report via the morning EMA survey and wearable actigraphy to measure and account for subjective biases in sleep timing. Craving reduction will be primarily measured using EMA assessment, and will be modeled using linear mixed models in the multilevel modeling (MLM) framework. In MLM, subject-specific random effects are combined with population-level fixed effects to account for variability both within each individual and between individuals in a manner that allows participants with incomplete data to be included in the model. Craving reduction will be modeled as an effect of time in treatment, and differences in rate of craving reduction will be tested as an interaction between treatment state and time. Drs. [name], [name], and [name] each have extensive experience analyzing similar data in the multilevel modeling framework.

For secondary safety outcomes, intensive longitudinal methods such as time-varying effect models will be used to assess for changes in continuously measured outcomes (e.g. blood pressure, heart rate, respiratory rate, body weight) to account for repeated measures. The proportion of participants experiencing AE and SAE will be compared between treatments using chi-square analysis.

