For exploratory outcomes, analysis of fNIRs-based neuroimaging will utilize a 2 (Medication Status) x 2 (Medication Type) ANOVA to evaluate the change in oxygenation in prefrontal cortex in response to opioid drug cues vs neutral cues, with a region of interest in left middle frontal gyrus. Analysis of safety outcomes from baseline to the end of target dose and to end of rebound follow-up will be analyzed using intensive longitudinal methods similar to the analysis of secondary outcomes. Changes in indices of glycemic control measured at baseline and at end of the target dose (e.g. HgA1c, fructosamine) will be calculated as deltas, with comparisons made between treatments using unpaired t-tests or Mann Whitney U tests as appropriate.

Interim Power Analysis: one or more interim power analyses may be conducted during the study to assess the effect size needed to observe a significant drug effect for primary, secondary, and/or exploratory endpoints based on the data collected at that time. These analyses would not bias type 1 error rates and the study team will use this information to determine whether and when to perform an interim data analysis to justify advancement to the second phase of the funding award (UH phase). In particular, the confidence intervals around the parameters representing the primary endpoint will be used as an approximation of the power available for our primary endpoints using the current data. This

will be weighed against the original proposed power and the PI's estimates of likely power after completion of the grant period to determine whether an interim analysis is warranted.

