9.4 Frequency of data collection

Primary outcome data for cue-elicited drug craving will be collected on the day before drug treatment (Day 1) and Day 19 (additionally Day 31 for the 5-dose intervention). Ambient drug craving data will be collected on test days and on the first two days and last 2 days of each treatment dose (Days 1-21 [Days 1-33 for 5-dose intervention]). Secondary outcome data for the physical/psychological screening will be collected on Day 1. Cardiorespiratory function data will be collected periodically throughout the study (Days 1, 2, 8, 14, 19, 21 [5-dose intervention: 1, 2, 8, 14, 20, 26, 31, 33]). HbA1c and fructosamine monitoring (blood draw) data will be collected on Days 2 and 19 [additionally Day 31 for 5-dose intervention]. See also table of study events, section 7.2.

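### Blood pressure, heart rate and respiratory rate are seen on only 6 or 9 days and have named-day endpoints, but the example method is a smooth time-varying curve with unstated smoothing, which can understate the off-drug change

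*Combined protocol and SAP*

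**What the plan says.** **Method.** Section 8.3 states that for the secondary safety outcomes "intensive longitudinal methods such as time-varying effect models will be used to assess for changes in continuously measured outcomes". Its examples are "e.g. blood pressure, heart rate, respiratory rate, body weight) to account for repeated measures". For the changes to end of target dose and to the rebound visit, the same section says the data "will be analyzed using intensive longitudinal methods similar to the analysis of secondary outcomes". It gives no basis, knots, penalty, on/off-drug term or day-specific contrast for these outcomes. ANCOVA and mixed models are specified for craving, and t-tests or Mann-Whitney tests for the glycemic markers, but neither for the vital signs.

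**Endpoints.** Section 1.3 defines the secondary endpoint as "Change in blood pressure from baseline (Day 1) to: i) the beginning of each study drug dose (Days 2, 8, 14, 20, 26"), then "ii) end of the target drug dose (Day 19 [Day 31 for 5-dose intervention]); and iii) rebound follow-up (Day 21 [Day 33 for 5-dose intervention"]), with parallel wording for heart rate and respiration. Section 1.4 adds the exploratory rebound endpoints, for example "Change in heart rate from end of the target drug dose (Day 19 [Day 31 for 5-dose intervention]) to rebound follow up".

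**Measurement days.** Footnote 3 of each schedule of activities gives Days 1, 2, 8, 14, 19 and 21 (3-dose) and Days 1, 2, 8, 14, 19, 20, 26, 31 and 33 (5-dose). Section 9.4 has a shorter 5-dose list, "5-dose intervention: 1, 2, 8, 14, 20, 26, 31, 33", which leaves out Day 19. Section 7.2 describes 15 minutes of continuous recording per session, so there are many readings within a day but no more days.

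**The concern.** A time-varying effect model estimates the arm difference as a smooth function of study day. It suits densely sampled series, such as body weight taken daily or heart rate from the wristband. Here the question is what happened at particular days, and the sharpest question concerns two days that are two days apart, one on drug and one off. A smooth curve borrows strength across that step. If it is flexible enough not to, it does little more than reproduce the day means. The plan does not say where between these the model will sit, so the reported rebound change would depend on a tuning choice made later.

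Safety is one of the two study objectives (Section 1.1), and demonstrated safety is a stated condition for a follow-on multi-center trial (Section 2.3). An understated cardiorespiratory change, with an interval that looks precise, would carry into that decision.

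**Working it through.** The plan gives no design figure for the vital signs. Its only power figure (Section 8.2, for craving) reproduces: 20 per group and an effect of 0.91 SD give 80.1% by the noncentral t. The 0.91 is borrowed below only as a scale.

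**Inputs from the documents.** The measurement days above, the named-day endpoints, and a 13-hour half-life (Section 10.0). Some 48 hours after the last dose, 0.5^(48/13) = 0.077, so about 8% of the drug remains. A step between Days 19 and 21 is therefore plausible.

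**Assumed.** All effect profiles and all smoothing levels. The documents give neither.

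**Check 1: polynomial curves, 3-dose days, no noise.** Fitted values are Hy with H = X(X'X)⁻¹X', where X holds powers of day. For the quadratic, the weights on Days 1, 2, 8, 14, 19, 21 are:

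- Day 19 estimate: −0.026, −0.019, 0.061, 0.198, 0.356, 0.431
- Day 21 estimate: 0.067, 0.002, −0.176, 0.005, 0.431, 0.671

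The Day 19 estimate gives more weight to the off-drug Day 21 value (0.431) than to Day 19 itself (0.356). With an assumed arm difference of 0, 2, 4, 6, 6, 1 bpm:

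- Day 19: −0.038 + 0.244 + 1.188 + 2.136 + 0.431 = 3.96 (true 6)
- Day 21: 0.004 − 0.704 + 0.030 + 2.586 + 0.671 = 2.59 (true 1)
- Drop: 3.96 − 2.59 = 1.37 (true 5)

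Drop from Day 19 to Day 21, varying only the Day 21 value:

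| Assumed Day 21 value | True drop | Quadratic | Cubic | Quartic |
|---|---|---|---|---|
| 1 bpm | 5 | 1.4 | 2.8 | 4.96 |
| 3 bpm | 3 | 0.9 | 1.7 | 3.18 |
| 6 bpm (effect persists) | 0 | 0.17 | 0.08 | 0.53 |

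**Check 2: natural cubic smoothing spline, 3-dose days.** Two assumed profiles, both zero on Days 1, 2 and 21: constant (1, 1, 1 on Days 8, 14, 19) and dose-proportional (1/3, 2/3, 1). Ranges cover both profiles. Coverage is for a true rebound difference of 0.91 SD with 20 per group, change-score SD 1 (residual variance 0.5), and SE = √(0.5 · a'a · 2/20), where a is the smoother's weights for the contrast.

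| Effective df | Day 19–21 change kept | Day 1–19 change kept | Coverage of nominal 95% interval, rebound | SE rebound | SE Day 1–19 |
|---|---|---|---|---|---|
| 3 | 13–24% | 56–62% | about 0% | 0.07 | 0.22 |
| 4 | 40–48% | 68–76% | 2–5% | 0.13 | 0.22 |
| 5 | 75–77% | 86–91% | 83–86% | 0.23 | 0.26 |
| 6 (one per visit) | 100% | 100% | 95% | 0.32 | 0.32 |

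The last row is what day as a category gives: √(0.5 · 2 · 2/20) = 0.32. Power for the rebound contrast ran from 43% to 91% under smoothing, against 82% (normal approximation) at 6 df. The harm is therefore mainly bias and coverage, not a consistent loss of power.

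**Check 3: 5-dose days.** The Day 31–33 change keeps 5–12% at 3 df, 31–36% at 5 df and 73–75% at 7 df.

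**Check 4: one curve pooled over both schedules.** Assume 20–50% extend and the effect is constant on drug. The Day 19–21 change keeps 2–5% at 3 df, 9–19% at 5 df and 60–77% at 8 df. Day 20 comes only from 5-dose participants, who are on drug (Section 7.2.6), and sits next to Day 21, which comes only from 3-dose participants off drug. Pooling spreads the curve over ten distinct days rather than six, so equal df are not equal flexibility, but the direction is clear.

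**The case against.** The strongest reply is that the text commits to nothing harmful. The words 'such as' make time-varying effect models an example, so another repeated-measures method is open to the analyst. Section 8.3 also promises that model assumptions and goodness of fit will be assessed, which could expose an over-smoothed curve. Blurring is not inevitable: the quartic, with five parameters for six days, recovers 4.96 of the 5 bpm, and an on/off-drug term would avoid the problem. The profiles are invented and ordinary polynomials are not the planned model.

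Much of this stands. A reader might infer that the plan fixes on smooth curves, that such curves must blur the endpoints, and that Day 19 is always pulled down and Day 21 up. The documents support none of these. With a persisting effect, the quadratic gives 6.11 on Day 19 and 5.94 on Day 21, almost unbiased. With 0, 0, 0, 2, 2, 2 bpm, a cubic invents a drop of 0.4.

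What the reply does not remove is the mismatch. Smooth time-varying models are the only method named for these outcomes, no contrast at a named day is specified, and the fit check has no stated criterion or consequence. The quartic's success on one profile and the spline's 75–77% at the same number of df show that the answer turns on unstated choices.

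**Conclusion.** The point holds as a mismatch between the example method and the endpoints, with a better-matched and inexpensive alternative. A low-flexibility curve can understate the 2-day rebound change substantially (13–48% kept at 3–4 df in the 3-dose schedule) and the Day 1 to Day 19 change less so (56–76% kept). Both losses shrink as flexibility rises and vanish at one df per visit. These figures assume an effect that has gone by the rebound day; they are not estimates of bias in this trial.

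A reader might also infer that the main safety endpoints, or participants' protection, are at risk. The documents do not say so. Cardiorespiratory function stands beside body weight, glycemic control and adverse events as secondary (Section 1.3), the rebound change is exploratory (Section 1.4), and Section 8.2 calls the study an exploratory pilot. Participants are protected by withdrawal thresholds (Sections 3.3.1 and 18.7), the medical monitor and the DSMB. The change is worth making before analysis, but it is not critical.

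**What to change.** In Section 8.3, for blood pressure, heart rate and respiratory rate, replace the time-varying effect model with a likelihood-based repeated-measures mixed model: day as a category, arm, arm-by-day, and the Day 1 value as covariate. Report arm differences with 95% CIs for:

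- each dose start (Days 2, 8 and 14, plus Days 20 and 26 for 5-dose);
- the end of the target dose (Day 19, or Day 31 for 5-dose);
- the rebound visit (Day 21, or Day 33 for 5-dose);
- the rebound contrast (Day 19 to 21 for 3-dose, Day 31 to 33 for 5-dose).

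Handle the two schedules separately after Day 19. Because extension is the participant's choice during treatment (Section 7.1), label those later comparisons as being within self-selected subsets. Bring the 5-dose day list in Section 9.4 into line with the schedule of activities on Day 19. Smooth models may be kept for daily body weight and wristband heart rate.

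The cost is SAP wording and no new data. Intervals will be wider than a smoothed curve would give: in the working above, SE 0.32 against 0.22–0.26 for the end-of-dose change and 0.07–0.23 for rebound. The narrowest of those smoothed intervals are centred on the wrong value.

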2.3 Study Rationale

The rationale for the proposed research is to develop an acute intervention that can improve treatment outcomes in OUD by reducing craving, a primary factor contributing to early relapse. Although liraglutide was approved for human use in 2010, there are no data testing the effectiveness in patients with an OUD. The objective of the proposed research is to test whether treatment with a GLP-1R agonist can reduce craving in humans with OUD. Understanding how a 'satiety' agent may affect craving and brain responses to drug cues in an OUD population would provide entirely novel information. If liraglutide shows a trend towards efficacy, and safety of the GLP-1R agonist is demonstrated in this population, it would provide an indication to run the second phase, multi-center clinical trial of GLP-1R agonist in OUD patients.

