7.4.3 Method for Assigning Subject to Treatment Groups

Participants will receive either liraglutide or placebo in a two-arm parallel group study. Interventions will be randomized in a 1:1 ratio using permuted-block randomization algorithm. The randomization will be performed using a random number generator via the PLAN procedure within SAS software, version 9.4 (SAS Institute Inc., Cary, NC). Personnel in the Department of Public Health Sciences (PHS) will use the PLAN procedure within SAS software to generate a randomization list using variable-size, random permuted blocks to ensure that the number of participants in each arm is balanced after each set of B randomized participants, where B is the block size. Personnel in PHS will choose the block sizes without revealing it to any of the investigators or study personnel who will be collecting and reviewing outcomes data. The randomization sequence will be uploaded to a secure REDCap database. Synergy Pharmacy will be given access to this REDCap database to provide the blinded, randomized labeling prior to shipping the study drugs to the CaronTC

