8.0 Subject Numbers and Statistical Plan

8.1 Number of Subjects

This study will enroll 50 opioid use disordered patients in residential treatment.

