8.2 Sample size determination

This is an exploratory study to accumulate pilot data. The primary endpoint of this study is cue-elicited self-reported craving VAS scores. A sample size of N=20 per group will give 80% power to detect an effect size of 0.91 based on a two-sided two-sample t-test with a significance level of alpha=0.05. Accounting for an estimated 20% attrition rate, we plan to randomize a total of 20*2/0.8=50 patients in the study. To preserve statistical power, the sample will not be balanced with regard to MAT and non-MAT participants.

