8.3 Statistical methods

The primary aim is to test whether liraglutide reduces craving in patients recovering from OUD in residential treatment. Analysis of covariance (ANCOVA) will be used to compare liraglutide versus placebo treatment groups controlling for baseline values of craving. Linear mixed effects models for repeated measurements will also be used to evaluate the difference in changes in these primary outcomes between treatment groups. The baseline and post-treatment outcomes are treated as dependent variables in the mixed model. Subjects with missing values can be incorporated in the mixed model analysis when data are missing at random. The moderating effect will be assessed by adding the interaction term between moderator and treatment group in the models.

SAS (version 9.4) and R (version 3.2.5) software will be used for analyses with a significance level of 0.05. Summary statistics including means, medians, ranges, and standard deviations will be computed for each continuous variable and frequencies with percentages for categorical variables. Identified data outliers will be further examined to determine if they are data entry errors, in which case they will be modified when possible; otherwise, values will be kept for final analysis.

Primary outcomes to assess efficacy are: (1) cue-elicited drug craving rated on a 100-pt VAS; and (2) ambient drug craving, derived from EMA of daily craving throughout the study period. Data analyses for cue-elicited craving will consist of a 2×2 ANOVA with medication status (pre- vs post-medication) as a within-group variable and medication type (liraglutide vs placebo) as a between-group variable.

Secondary analyses of self-reported craving measures will evaluate the role of MAT, specifically BUP/NA, in these results.

EMA and Wearable Assessment: Ambient drug craving derived from the EMA will be analyzed as a multilevel model in the regression framework and will test effects of medication status within-person and medication type between-person. Secondary analyses of EMA will examine the effect of time (e.g. study day) to identify differences across condition in the rate of decline in craving across time.

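### Chi-square is the only planned AE/SAE comparison in about 25 per arm; for sparse SAE tables it is unreliable or undefined, and no interval is planned to carry the safety conclusion

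*Combined protocol and SAP*

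**What the plan says.** Section 8.3 gives one rule for adverse events: "The proportion of participants experiencing AE and SAE will be compared between treatments using chi-square analysis". It fixes the level for all analyses, stating that the software "will be used for analyses with a significance level of 0.05". It promises frequencies and percentages for categorical variables, so arm proportions are covered. It names no exact test, no interval for the difference between arms and no rule for a table with few or no events. It does say that model assumptions will be assessed, but attaches no alternative for sparse counts. For the glycemic indices, by contrast, the same section allows a parametric or a rank test according to the data.

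On size, Section 8.1 states "This study will enroll 50 opioid use disordered patients in residential treatment" and Section 7.4.3 "Interventions will be randomized in a 1:1 ratio using permuted-block randomization algorithm", so about 25 per arm. Section 8.2 derives this from cue-elicited craving alone, using a two-sided t-test at the 5% level: "A sample size of N=20 per group will give 80% power to detect an effect size of 0.91". No expected rate, margin or power is given for AEs or SAEs.

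Section 2.3 says a multi-center trial would be indicated if there is a trend towards efficacy "and safety of the GLP-1R agonist is demonstrated in this population". The rationale of the sleep sub-study (Section 23.0) repeats this condition, and Section 7.1 says safety will be established. None of the three gives a criterion.

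**The concern.** Pearson's chi-square takes its p-value from a large-sample approximation that needs adequate expected counts in every cell. AEs of any kind may be common enough for that. SAEs in 50 patients followed for a few weeks probably are not. Two consequences follow. The p-value in a table with three to five SAEs can fall on either side of 0.05 depending on which reasonable test is used, so the choice should be made before the data are seen. And if there is no SAE, the one planned between-arm comparison produces nothing.

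Safety is the study's secondary objective (Section 1.3). As written, the plan could reach the end of the trial with no between-arm AE/SAE statement that carries its uncertainty, while the rationale uses words for safety that a trial of this size cannot support without stating what rate it has excluded.

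**Working it through.** **Inputs.** From the documents: 50 randomized, 1:1, so 25 per arm; 20 per arm after the 20% attrition in Section 8.2; alpha 0.05. Sections 3.3.2 and 3.3.3 allow withdrawn participants to be replaced, so 25 is approximate. All event rates below are assumptions, because the documents give none.

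**The plan's own figure.** Noncentral-t power for a two-sided t-test with 20 per arm, d = 0.91 and alpha 0.05 is 80.1%, and 40/0.8 = 50. The stated size is reproduced. It concerns craving only.

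**Expected counts.** With equal arms and T participants with an event in total, the expected event cell is T/2. This is at least 5 only if T ≥ 10, which is 10/50 = 20% overall at 25 per arm and 10/40 = 25% at 20 per arm.

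**How often the condition fails.** With the same rate p in both arms, T is Binomial(50, p). The chance of no event is (1 − p)^50. Size is found by enumerating all 25-versus-25 tables, with no-event tables counted as non-rejections.

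| Assumed rate | P(T < 10) | P(T = 0) | Actual size of chi-square |
|---|---|---|---|
| 1% | >99.9% | 60.5% | 0.02% |
| 2% | >99.9% | 36.4% | 0.2% |
| 5% | 99.98% | 7.7% | 2.0% |
| 10% | 97.5% | 0.5% | 4.9% |

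For any-AE tables, P(T < 10) is 4.0% at a 30% rate and about 0% at 50%.

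**The p-value depends on the test.** For 4/25 versus 0/25:

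- Chi-square = 50 × (4×25 − 0×21)² / (25×25×4×46) = 500,000/115,000 = 4.35, p = 0.037.
- Fisher = 2 × C(25,4)/C(50,4) = 2 × 12,650/230,300 = 0.110.
- Boschloo's exact unconditional test: p = 0.065.

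For 5/25 versus 0/25 the values are 0.018 (chi-square), 0.033 (Boschloo) and 0.0502 (Fisher).

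**Power, assumed 2% versus 15%, 25 per arm, by the same enumeration.** Chi-square 37%, Fisher 12%, Boschloo about 22%. At 2% versus 10%, chi-square has 15.3% and Fisher 2.3%.

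**What the size can exclude.** With no SAE among n participants, the two-sided 95% upper limit is 1 − 0.025^(1/n): 13.7% for n = 25 and 16.8% for n = 20. Newcombe 95% intervals for the risk difference at 25 per arm:

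- 0 versus 0: −13.3 to +13.3 points.
- 1 versus 0: −9.7 to +19.5 points.
- 4 versus 0: the Wilson limits are 6.4% to 34.7% for 4/25 and 0 to 13.3% for 0/25. The lower limit is 16.0 − √(9.6² + 13.3²) = −0.4 points, and the upper limit is +34.7 points.

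**The case against.** The strongest reply is that this is a declared exploratory pilot, that AEs and SAEs are secondary, and that no action is tied to the p-value. Safety is also followed by the DSMB, the medical monitor, laboratory tests and vital signs (Sections 8.3, 9.3, 9.5 and 9.6). That is true and keeps the point modest. But a pilot is better served by estimates with intervals than by a bare test, and none of those other sources supplies a between-arm AE/SAE comparison.

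Three stronger readings are tempting, and the documents do not support them.

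- A reader might infer that a non-significant chi-square will be taken as proof of safety. No section says so. Sections 2.3, 7.1 and 23.0 name no test or threshold. The part of Section 8.3 on advancing to the second funding phase refers to confidence intervals for the primary endpoint, not to the AE comparison. What stands is that the criterion is undefined.
- A reader might infer that chi-square rejects too often for SAEs. At common rates of 1% to 10% its actual size is 0.02% to 4.9%, so it does not exceed 5%. A split as extreme as 4 versus 0 is itself rare when the arms share a low rate.
- A reader might extend the objection to every AE table. At any-AE rates of about 30% to 50% the expected-count condition is nearly always met. It would fail at the other end only if fewer than 10 of the 50 were event-free.

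It is also fair to object that an exact test makes it harder to flag harm. At the assumed 2% versus 15%, Fisher's power is 12% against 37% for the planned chi-square. This stands. It is the reason to prefer Boschloo to Fisher and to let the interval, not the p-value, carry the conclusion.

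**Conclusion.** The point holds for SAEs and other sparse AE categories. For assumed overall rates of 1% to 10%, the chi-square condition fails with probability 97.5% or more at 25 per arm. The test cannot be computed with probability 60% at a 1% rate, 36% at 2% and 8% at 5%. When a few SAEs do occur, the choice of test can decide significance. The SAE rates are assumptions, but the condition fails whenever fewer than 10 of 50 participants have the event, so the result is not sensitive to the exact rate within that range.

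The trial is sized on craving, so the size is not an error. It does limit what can be said about safety: even a liraglutide arm of 25 with no SAE is compatible with a true rate of up to 13.7%. The words *demonstrated* and *established* need either a criterion or a statement of that limit. This is a modest change to a secondary analysis, worth making before the data are unblinded.

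**What to change.** In Section 8.3:

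1. For SAEs, and for any AE category with an expected count below 5, replace chi-square by a named exact test fixed in advance. Boschloo's test is suggested as less conservative than Fisher's. Chi-square may stay for common AE categories.
2. For AEs and SAEs, report the number and proportion per arm and the risk difference with a 95% score (Newcombe) or exact interval, as the main AE/SAE summary. State that this is reported even when no event occurs, and that the absence of a significant difference is not itself a finding of safety.

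In Sections 2.3, 7.1 and 23.0, either define what would count as safety demonstrated or established, or replace those words by the rate the data exclude. For example, no SAE in 25 on liraglutide excludes a rate above 13.7% (16.8% if 20 are evaluable) at the two-sided 95% level.

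The cost is a few sentences, with no new data, visits or participants. The downsides are that the exact test rejects less often than chi-square and that the safety statement becomes more guarded.
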